### **7.2.11 Twelve-lead Electrocardiogram (ECG)**

Twelve-lead ECGs will be performed at the times specified in [Table 1](#) by appropriately delegated study staff. The following parameters will be recorded on the appropriate CRF page: heart rate,

rhythm, PR, RR, QRS, and QT intervals, and any wave form abnormalities. The QT interval corrected for heart rate by Fridericia's formula (QTcF) will be from the Investigator's read. The Investigator's assessment of the ECG tracing as normal or abnormal must be documented. If the Investigator feels that the ECG is abnormal, he/she needs to determine if the abnormality is significant or not. Overall, ECG significance is to be documented on the tracing and recorded in the CRF.

The subject will be asked to remove all clothing that covers the location of lead placement. The subject should not have exercised or consumed caffeine, alcohol, or nicotine within 30 minutes of collection. The subject must be resting in the supine position for at least 5 minutes before collecting the ECG.

In some cases, it may be appropriate to repeat abnormal ECGs to rule out improper lead placement as contributing to the ECG abnormality. It is important that leads are placed in the same positions each time to achieve precise ECG recordings.

A single ECG recording, including a 10-second rhythm strip, will be obtained for all assessments. ECG results will be recorded in the CRF. The ECG recording should be immediately assessed to verify that it is a valid recording and if not valid, it should be repeated to obtain a valid recording. Invalid recordings will not be entered in the CRF.

To ensure the safety of the subjects, a qualified individual at the Investigator site will make comparisons to baseline measurements.

If a machine-read QTcF value is prolonged, repeat measurements may not be necessary if a qualified physician's interpretation determines that the QTcF values are in the acceptable range.

## 7.2.12 Pharmacokinetic Procedures

The name and address of the bioanalytical laboratory performing the PK assessment for this study will be maintained in the Investigator's files at the/each site and in the Trial Master File at BioAge Labs.

Actual PK blood sample collection times versus time of dosing will be monitored. The time of meal will also be captured, as dosing should occur within 30 minutes of eating. The BioAge Labs expectation is that the Investigator will ensure that every effort is made to collect all PK blood samples at the precise protocol scheduled time. Pre-dose (trough) pharmacokinetic blood collection should be collected within 30 minutes prior to the dose. If subjects are being dosed at home, the subject should be instructed to not dose until the home health visit is conducted. Post-dose (peak) PK blood samples should be collected between 3 and 6 hours after the daily dose. Samples drawn outside these parameters will be considered a protocol deviation.

### 7.2.12.1 Blood Sample Collection and Handling Procedures

Pharmacokinetic blood samples will be collected at the times specified in [Table 1](#) to measure plasma concentrations of asapiprant and metabolites thereof. A full description of PK blood collection, handling, storage and shipping can be found in the provided laboratory manual.

Plasma sample tubes for bioanalysis must be freezer-safe and identified with freezer-safe labels provided by the CPU. The labels will contain the following information:

- Study number (BGE-175-201)
- Subject identifier (This number consists of a 5-digit number. The first digit will identify the Study Part the subject is assigned to; the second and third digit will identify the cohort number that the subject is assigned to within the study part; and the fourth and fifth digits will identify the subject number within a cohort).
- Nominal day (e.g., Day 1)
- Nominal time (e.g., predose)
- Matrix identifier (plasma)
- Split (primary or back-up).

#### **7.2.12.2 Shipment of Plasma Pharmacokinetic Samples**

Instructions for shipment of PK samples (along with the corresponding documentation) can be found in the laboratory manual, provided separately.

Pharmacokinetic samples will be stored nominally at -70°C or below prior to and after analysis at the CRO until further directions are authorized by the Sponsor (or a nominated designee).

#### **7.2.12.3 Plasma Drug Assay Methodology**

Plasma sample analysis will be performed according to relevant Sponsor (or a nominated designee) Standard Operating Procedures.

Plasma concentrations will be measured using the most current validated bioanalytical method. In addition, selected plasma samples may be used to investigate incurred sample reproducibility (full details will be described in the bioanalytical study plan). Raw data will be stored in the archive of the designated bioanalytical contract laboratory.

### **7.2.13 Pharmacodynamic Assessments**

The name and address of the bioanalytical laboratory performing the PD assessment for this study will be maintained in the Investigator's files at the/each site and in the Trial Master File at the Sponsor.

Actual PD blood sample collection times versus time of dosing will be monitored. The Sponsor's expectation is that the Investigator will ensure that every reasonable effort is made to collect all PD blood samples at time points in [Table 1](#).

A blood sample to assess proteomics, metabolomics, and transcriptomics will be collected at Day 1 and at the End of Treatment visit as described in [Table 1](#).

#### **7.2.13.1 Blood Sample Collection and Handling Procedures**

Pharmacodynamic blood samples will be collected at the times specified in the laboratory manual to measure plasma concentrations. A full description of PD blood collection, handling, storage and shipping can be found in the provided laboratory manual.

Plasma sample tubes for bioanalysis must be freezer-safe and identified with freezer-safe labels provided by the central lab. The labels will contain the following information:

- Study number (BGE-175-201)
- Subject identifier
- Nominal day (e.g., Day 1)
- Nominal time (e.g., predose)
- Matrix identifier (e.g., plasma)
- Split (primary or back-up).

#### 7.2.13.2 Shipment of Plasma Pharmacokinetic and Pharmacodynamic Samples

Instructions for shipment of PK and PD samples (along with the corresponding documentation) can be found in the laboratory manual, provided separately.

Pharmacodynamic samples will be stored nominally at -70°C or below prior to and after analysis at the CRO until further directions are authorized by the Sponsor (or a nominated designee).

#### 7.2.14 Volume of Blood to be Drawn from Each Subject

During this study, it is expected the total volume of blood taken will not exceed 500 mL for any subject in any part of the study, regardless of sex.

The amount of blood to be drawn for each assessment is an estimate. The amount of blood to be drawn may vary according to the instructions provided by the manufacturer or laboratory for an individual assessment. When more than 1 blood assessment is to be done at the same time point/period, if they require the same type of tube, the assessments may be combined.

[Table 3](#) provides the estimated volume of blood to be drawn for each subject.

**Table 3: Estimated Volume of Blood to be Drawn from Each Subject**

Assessment		Sample Volume (mL)	Number of Samples	Total Volume (mL)
Pharmacokinetic samples a		4	7	28
Pre-dose Serological markers - PGD2		4	1	4
Blood for Inflammation markers b		4	10	40
Proteomic, metabolomic, and transcriptomic samples		4	2	8
Safety	Biochemistry c	8.5	6	51
	Coagulation (PT, aPTT, INR)	3	6	18
	Hematology	3	6	18
Total				167 mL

HBsAg = hepatitis B surface antigen; HCV = hepatitis C virus; HIV = human immunodeficiency virus; TSH = thyroid stimulating hormone

a If a catheter is used for any blood draw or series of blood draws, then the first 1 mL is to be discarded. The 1-mL discard has been taken into account in the table above and the total blood volume required for this study.

- b Two 2.7-mL samples are to be drawn for each pharmacodynamics blood sampling time point.
- c Serology panel (HBsAg, HIV, HCV), and thyroid panel (TSH) will be included in the biochemistry panel and collected at screening only.

## **8 DATA MANAGEMENT AND STATISTICAL METHODS**

### **8.1 Data Collection**

A validated EDC System will be used during study conduct. The Investigators' authorized site personnel must enter the information required by the study CRF Completion Guidelines or similar for all data requiring transcription of the source. This study will be monitored according to ICH GCP Guidelines.

A study monitor will visit each site in accordance with the monitoring plan and review the CRF data against the source data for completeness and accuracy. Discrepancies between source data and data entered on the CRF will be addressed by qualified site personnel. When a data discrepancy warrants correction, the correction will be made by authorized site personnel (in an auditable manner). Data collection procedures will be discussed with the site at the site initiation visit and/or at the Investigator's meeting. Once a subject is randomized, it is expected that site personnel will complete the CRF entry within approximately 3 business days of the study visit date.

### **8.2 Clinical Data Management**

Data are to be entered into a clinical database as specified in the Data Management Plan and according to the study CRF Completion Guidelines. Quality control and data validation procedures are applied to ensure the validity and accuracy of the clinical database.

Data are to be reviewed and checked for omissions, errors, and values requiring further clarification using computerized and manual procedures. Data queries requiring clarification are to be communicated to the site for resolution. Only authorized personnel will make corrections to the clinical database, and all corrections are documented in an auditable manner.

### **8.3 Data Handling**

Data that may potentially unblind the treatment assignment (e.g., IP serum concentrations, treatment allocation, and IP preparation/accountability data) will be handled with special care during the data cleaning and review process. Unless otherwise specified, these data will be handled in such a way that, prior to unblinding, any data that may unblind study team personnel will be presented as blinded information or otherwise will not be made available. If applicable, unblinded data may be made available to quality assurance representatives for the purposes of conducting independent drug audits.

All analyses/summaries will be based on observed data, with no imputation for missing data, unless otherwise specified in the statistical analysis plan (SAP).

### **8.4 Statistical Analysis Process**

The study will be analyzed by the Sponsor (or a nominated designee).

The primary endpoint (proportion who have died or progressed to RF at Day 28) will be analyzed using a logistic regression with treatment group and covariates, age group (50 to <75 years, and > 75 years), baseline WHO ordinal clinical scale (3 or 4), and region. Other covariates including previous COVID-19 therapy may be explored. Estimation of the covariate-

adjusted difference in proportion responding will be reported using Cochran-Mantel-Haenszel (CMH) weighting and estimates from the logistic regression (LR) as described by Ge and colleagues (Ge et al., 2011, Appendix C). This analysis will be repeated without the covariate. Deaths prior to Day 28 will be included in the endpoint (RF, death). WHO Ordinal Scale for COVID-19 scores ([Table 2](#)) will be analyzed by carrying forward any early deaths through Day 28; other categorical and continuous outcomes will be described. The primary analysis will be based on the Intent-to-Treat population (ITT), analyzed as randomized. The denominator for the proportions alive and RF-free at Day 28 will include all randomized subjects. Subjects lacking sufficient data to confirm RF-free and alive at Day 28 will be included in the primary analysis as treatment failures. If more than 5% of subjects have insufficient data to confirm RF-free and alive at Day 28, BioAge will employ a MI strategy (SAS MI, MIANALYZE) based on the patients last known status. For example, the last known WHO Score for a patient lost to follow-up can be used to impute missing primary outcome from patients with known primary outcome and similar WHO Scores. For the primary comparison, analysis by treatment group will be, “as randomized”. Secondary analyses of the primary endpoint may be repeated for the mITT and the per protocol populations, analyzed as treated. Time-to-RF will be analyzed using methods of Kaplan-Meier (KM), with time zero at randomization. Hazard ratios (Cox PHREG) with 95% confidence intervals will describe the treatment effect.

A sensitivity analysis may be completed to assess concurrent treatments and prior SARS-CoV-2 vaccinations in relation to the primary endpoint.

Secondary endpoints that are proportions will be analyzed like the primary endpoint, using logistic regression with and without the designated covariates and by FET. 95% confidence intervals and p-values (without correction) will be presented for these descriptive analyses. Time-to-event analyses will use the methods of Kaplan-Meier with censoring rules for the different endpoints provided in the SAP. Descriptive statistics for TTE will be median times to event with 95 confidence intervals and log-rank statistics to test for treatment differences; Cox proportional hazards with 95% CI will be presented.

“Incidence and duration” secondary endpoints will be analyzed by counting days per subject and then forming 95% confidence intervals and Wilcoxon tests and t-tests to compare treatments. Incidence will also be compared using FET.

These analyses of secondary endpoints will be done using the ITT population and may be repeated for the mITT and PP populations.

No secondary endpoints are designated as, “key” for any labeling purposes.

Results of secondary endpoint analyses will not be corrected for multiplicity.

The Sponsor does not intend formal statistical analyses for safety data. However, odds ratios (95% CI) for common adverse events will be displayed.

The SAP will further describe the statistical methods and definitions for the analysis of the efficacy endpoints, PK, PD, and safety data, as well as describe the approaches to be taken for summarizing other study information, such as subject disposition, demographics and baseline characteristics, IP exposure, and prior and concomitant medications. The SAP will also include further description of how missing and spurious data will be addressed.

To preserve the integrity of the statistical analysis and study conclusions, the SAP will be finalized prior to the IA. Analysis rules and methods for the IA are planned to be the same as the rules and methods for the final analysis.

Unless noted otherwise, all statistical analyses will be performed using SAS® Version 9.3 or later (SAS Institute, Cary, NC 27513).

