## 2.3 Endpoints

### 2.3.1 Primary Endpoint

Proportion of subjects who have died or progressed to RF as defined by progressing to the need for high-flow nasal cannula O2 delivery, noninvasive positive pressure ventilation, invasive mechanical ventilation, or extracorporeal membrane oxygenation (ECMO) therapy at Day 28.

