## **8.6 Sample Size Calculation and Power Considerations**

Assuming a 31% RF rate in the placebo group and a 15% RF rate in the asapiprant group, for a Fishers Exact test with two-sided 5% Type 1 error and 90% power, the sample size to detect a 16% absolute improvement in the primary endpoint is 312 subjects (1:1 randomization). Randomization will be stratified based on the region within which a subject is enrolled (North America vs. South America) and age (50 to < 75 vs.  $\geq$  75 years of age).

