### Serious Adverse Event

A serious adverse event (SAE) is any untoward medical occurrence (whether considered to be related to investigational product or not) that at any dose:

- Results in death
- Is life-threatening.

Note: The term ‘life-threatening’ in the definition of “serious” refers to an event in which the subject was at risk of death at the time of the event; it does not refer to an event which hypothetically might have caused death if it was more severe.

- Requires inpatient hospitalization or prolongation of existing hospitalization. Note: Hospitalizations, that are the result of elective or previously scheduled investigations procedures or surgery for pre-existing conditions and have not worsened after initiation of treatment, should not be classified as SAEs. For example, an admission for a previously scheduled ventral hernia repair would not be classified as an SAE; however, complication(s) resulting from a hospitalization for an elective or previously scheduled surgery that meet(s) serious criteria must be reported as SAE(s).

- Results in persistent or significant disability/incapacity
- Results in a congenital abnormality/birth defect
- Is an important medical event.

Note: Important medical events that may not result in death, be life-threatening, or require hospitalization may be considered an SAE when, based upon appropriate medical judgment, they may jeopardize the subject and may require medical or surgical intervention to prevent 1 of the outcomes listed in this definition. Examples of such medical events include bronchospasm associated with anaphylaxis requiring intensive treatment in an emergency room or at home; blood dyscrasias or convulsions that do not result in inpatient hospitalization; or the development of drug dependency or drug abuse.

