### 3 ASSESSMENT OF ADVERSE EVENTS

#### Severity Categorization

The severity of AEs must be recorded during the course of the event including the start and stop dates. Events that increase in severity will have the severity updated and the highest severity will be assigned to the event. Worsening medical conditions, signs or symptoms present prior to initiation of investigational product, must be recorded as new AEs.

For example, if a subject reports mild intermittent dyspepsia prior to initiation of dosing with the investigational product, and the dyspepsia becomes severe and more frequent after first dose of a new AE of severe dyspepsia (with the appropriate date of onset) should be documented in the source.

The Investigator will assess the Grade of the AE per the NCI-CTCAE version 5.0 or higher.

Toxicities that are not specified in NCI-CTCAE will be defined as follows:

- Grade 1: mild; asymptomatic or mild symptoms; clinical or diagnostic observations only; intervention not indicated
- Grade 2: moderate; minimal, local, or noninvasive intervention indicated; limiting age-appropriate instrumental activities of daily living (ADL)
- Grade 3: severe or medically significant but not immediately life-threatening; hospitalization or prolongation of hospitalization indicated; disabling; limiting self-care ADL
- Grade 4: life-threatening consequences; urgent intervention indicated
- Grade 5: death related to AE

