11.1 Adverse events

Adverse events will be coded using MedDRA version 23.1 and will be graded according to the NCI-CTCAE version 5.0. AE summaries will be presented by primary SOC and PT.

Treatment-emergent Adverse events will be considered as any event or worsening of event with onset on or after receiving the first dose of study drug through Day 57.

Summaries will be presented by actual treatment and overall using the SAF. Although a PT or SOC may be reported more than once for a patient, each patient will only be counted once.

Number and frequencies of patients with TEAEs as well as number of events will be given by SOC and by PT within each SOC for the following:

- All TEAEs by treatment group
- Serious TEAEs by treatment group
- All TEAEs considered related by treatment group
- Serious TEAEs considered related by treatment group

QMS Document Name: Statistical Analysis Plan	Page 23 of 27
QMS No (include version ref): STF-015-GL.02	Document date: 09JUL2019
CONFIDENTIAL	

- All TEAEs by maximum severity and by treatment group
- TEAEs leading to death by treatment group
- TEAEs leading to study discontinuation of study drug by treatment group

Additionally, number and frequencies of patients with TEAEs as well as number of events will be presented by decreasing frequency for all TEAEs, serious TEAEs and TEAEs considered at least possibly related.

If severity is missing, the event will be graded as severe unless the event being recorded is leading to life-threatening or death and will be graded accordingly as grade 4 (life-threatening) or 5 (death). If relationship to study drug is missing, the event will be assessed as unrelated if it started before start of IMP; in all other cases it will be assumed to be related.

Patient listings will be provided for patients with adverse events, treatment emergent adverse events, serious adverse events, for all patients with adverse events leading to withdrawal of IMP, and for all adverse events leading to death.

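### The pooled AE and SAE totals include COVID-19 progression and no total without it is planned, so strong efficacy could mask an excess of other serious events

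*Protocol*

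**What the plan says.** The primary endpoint in Protocol 2.3.1 is "Proportion of subjects who have died or progressed to RF as defined by progressing to the need for high-flow nasal cannula" or a higher level of ventilatory support, assessed at Day 28.

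The safety definitions are general:

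- Protocol Appendix 3, Severity Categorization: "Worsening medical conditions, signs or symptoms present prior to initiation of investigational product, must be recorded as new AEs". Protocol 7.2.1.1 likewise treats worsening of a preexisting condition as an AE.
- Appendix 3, Serious Adverse Event: an event is serious, related or not, if among other criteria it is fatal, is life-threatening or "Requires inpatient hospitalization or prolongation of existing hospitalization". Every participant is in hospital at entry.
- SAP 11.1 counts TEAEs from first dose through Day 57, which covers the Day 28 endpoint window in treated patients.

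Neither document exempts COVID-19 progression or endpoint events.

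On reporting, Protocol 8.8 asks for TEAE counts overall as well as by system organ class (SOC) and preferred term (PT). SAP 11.1 states: "Number and frequencies of patients with TEAEs as well as number of events will be given by SOC and by PT within each SOC". It applies this to all, serious, related, serious related, maximum-severity and fatal TEAEs. No table sets progression terms aside. Protocol 8.4 plans no formal safety testing and adds: "However, odds ratios (95% CI) for common adverse events will be displayed". SAP 11.1 contains no odds ratios, and SAP section 1 says the SAP prevails over the protocol.

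**The concern.** A patient who progresses to ventilation or dies of COVID-19 counts once as an efficacy failure and, in most cases, again as a patient with a serious TEAE. The pooled totals then carry the efficacy result inside them. If the drug prevents progression, the any-SAE total falls on asapiprant even when other serious events rise. If it does not, a large equal block of progression events in both arms dilutes the difference.

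This matters more here because the protocol knows of no AE of special interest for asapiprant (7.2.1.2) and sets no drug-specific stopping criteria beyond the Child-Pugh rule (4.5). With no named toxicity to look for, an all-cause total is a natural place to notice a diffuse excess.

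**Working it through.** **The plan's own figure.** Protocol 8.6 starts from these rates: "Assuming a 31% RF rate in the placebo group and a 15% RF rate in the asapiprant group". The planned test is Fisher's exact, two-sided at the 5% level, and the target power is 90%. With mean rate 0.23 and difference 0.16:

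- Uncorrected: n = [1.960·√(2·0.23·0.77) + 1.2816·√(0.31·0.69 + 0.15·0.85)]² / 0.16² = 143.3, so 144 per arm (288 in total).
- Continuity-corrected: (143.3/4)·[1 + √(1 + 4/(143.3·0.16))]² = 155.5, so 156 per arm. That gives the stated 312. Exact Fisher power at 156 per arm is 90.5%.

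**Inputs.**

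- r: endpoint rate, 31% placebo and 15% asapiprant (Protocol 8.6). That section calls it an RF rate but applies it to the primary endpoint.
- s: share of endpoint events reported as serious. Not in the documents; varied from 30% to 100%.
- x: rate of other, non-progression SAEs. Not in the documents; assumed 5% placebo and 12% asapiprant, independent of progression.

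**Formula.** P(any SAE) = 1 − (1 − s·r)(1 − x).

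**Reference.** Other SAEs alone: OR = (0.12/0.88)/(0.05/0.95) = 2.59 (95% CI 1.09 to 6.17 at 156 per arm).

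**All endpoint events serious.** Placebo 1 − 0.69·0.95 = 34.5%; asapiprant 1 − 0.85·0.88 = 25.2%. OR = (0.252/0.748)/(0.3445/0.6555) = 0.64 (95% CI 0.39 to 1.05).

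| Endpoint rate, placebo vs drug | Share serious | Any SAE, placebo | Any SAE, drug | OR |
|---|---|---|---|---|
| 31% vs 15% | 100% | 34.5% | 25.2% | 0.64 |
| 31% vs 15% | 70% | 25.6% | 21.2% | 0.78 |
| 31% vs 15% | 50% | 19.7% | 18.6% | 0.93 |
| 31% vs 15% | 30% | 13.8% | 16.0% | 1.18 |
| 31% vs 25% | 100% | 34.5% | 34.0% | 0.98 |
| 31% vs 31% | 100% | 34.5% | 39.3% | 1.23 |

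**Where the direction flips.**

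- At planned efficacy, set (1 − 0.31s)·0.95 = (1 − 0.15s)·0.88. Then s = 0.07/0.1625 = 43%. The total reverses only if more than about 43% of endpoint events are reported as serious.
- With all endpoint events serious, the drug-arm endpoint rate must be below 1 − 0.6555/0.88 = 25.5%.
- With all serious and planned efficacy, the drug-arm rate of other SAEs at which the totals tie is 1 − 0.6555/0.85 = 22.9%. For placebo rates of 2% to 10% the tie lies between 20% and 27%.

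**Other assumed rates.** With other SAEs of 10% versus 20% and all endpoint events serious, any SAE is 37.9% versus 32.0%. The OR goes from 2.25 to 0.77. If progression and other SAEs never occur in the same patient, the totals are 41% versus 35%, again OR 0.77.

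**What does not move.** At PT level, respiratory failure occupies its own row, about 48 versus 23 of 156 (OR 0.39). The row for a different event keeps its own odds ratio.

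**The case against.** A reader might infer that every safety table and every AE odds ratio restates the primary result. The documents do not support that.

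- PT rows for other events, and SOC rows that hold no progression terms, are untouched.
- Related and serious related TEAEs have their own tables in SAP 11.1. Progression enters these only when judged related or when causality is missing.
- SAP 11.2 splits deaths by principal cause, so fatal COVID-19 can be separated from other deaths.
- Laboratory, ECG and most vital-sign summaries do not count AEs, although SpO2 follows the disease.
- The odds-ratio sentence in Protocol 8.4 reads most naturally event by event, so it is not itself the fault.

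Two further points carry weight. No passage says that endpoint events are SAEs; it follows from general definitions. Protocol 2.3.1 sets no flow threshold for high-flow oxygen, so an investigator may judge some endpoint events non-serious. The table specifications and the DMC charter are separate documents and could contain a split.

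All of this narrows the point to the pooled totals without removing it. PT rows spread a diffuse toxicity over small counts. Related-event tables rest on causality judgement in very sick patients, under two guides that differ. The Appendix 3 definition of a related event requires that the medical condition cannot explain it, whereas the WHO-UMC Possible category, which counts as related, includes events the disease could explain. Deaths by cause do not cover non-fatal SAEs.

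**Conclusion.** The point holds for the pooled any-TEAE, serious-TEAE, maximum-severity and fatal-TEAE totals, and no further. In those totals a non-progression odds ratio of 2.59 can appear as 0.64 under full planned efficacy with every endpoint event serious. It appears as 0.93 if half are serious and 0.98 with efficacy of 31% versus 25%. The direction stays correct, though attenuated, at 1.18 if 30% are serious and 1.23 with no efficacy. Masking is therefore possible but not certain. Reversal needs strong efficacy, a large share of endpoint events reported as serious, and an excess of other SAEs below the tie point. It is also most likely to be missed when the excess is too diffuse to show in its own rows.

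The rates of other SAEs, the share serious and independence are assumptions. The confidence intervals use the planned 156 per arm, and the SAP Addendum records that enrollment stopped before the interim analysis. The added summaries are a worthwhile improvement to a descriptive safety analysis, not the correction of an invalid one. The mismatch between Protocol 8.4 and SAP 11.1 on odds ratios is a separate and plain inconsistency.

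**What to change.** 1. In SAP 11.1, fix under blind a MedDRA preferred-term list for COVID-19 progression (for example respiratory failure, ARDS, hypoxia, worsening COVID-19 or COVID-19 pneumonia, fatal COVID-19). Repeat the pooled all-TEAE, serious-TEAE, maximum-severity and fatal-TEAE summaries without those terms, beside the full tables.
2. Reconcile Protocol 8.4 with SAP 11.1 on AE odds ratios. Add them to the SAP with 95% CIs, including pooled non-progression TEAEs and non-progression SAEs.

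The cost is a paragraph of SAP text, one blinded term review and a few repeat tables. SAP version 5.0 was itself revised after a blinded data review, so such a list was feasible then. If treatment codes have since been opened, the list should be labelled post hoc. The downside is that a drug-caused respiratory event would sit among the excluded terms, which is why both versions must be shown.
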